4.5.2 Dexamethasone

Dexamethasone for subjects in the EPd cohort will be administered as indicated in Table 4.5.2-1.

Age	Day	1	8	15	22
Cycles 1 and 2					
\leq 75 years old	Dexamethasone (mg)	28 mg PO + 8 mg IV ^{a,b}			
> 75 years old	Dexamethasone (mg)	8 mg PO + 8 mg IV ^{a,b}			
Cycles 3 and beyo	ond				
\leq 75 years old	Dexamethasone (mg)	28 mg PO + 8 mg IV ^{a,b}	40 mg PO per week ^c	40 mg PO per week ^c	40 mg PO per week ^c
> 75 years old	Dexamethasone (mg)	8 mg PO + 8 mg IV ^{a,b}	20 mg PO per week ^c	20 mg PO per week ^c	20 mg PO per week ^c

Table 4.5.2-1:Dexamethasone Dosing, EPd Cohort

¹ On days of elotuzumab, infusion dexamethasone will be administered as a split dose of:

28 mg PO, for subjects \leq 75 years old or 8 mg PO for subjects > 75 years old (between 3 - 24 hours before the start of elotuzumab infusion)

8 mg IV (on the day of elotuzumab infusion at least 45 minutes before the start of infusion)

^b If elotuzumab dosing is skipped or discontinued, dexamethasone will be administered orally as in days without elotuzumab.

^c Note the dexamethasone dose, as elotuzumab is not given on Days 8, 15 and 22 of cycle 3 and beyond.

AND

At the investigator's discretion, the oral dexamethasone may be given as a split dose over 2 consecutive days. Dexamethasone delay should be performed as clinically indicated at the discretion of the investigator.

Dexamethasone for subjects in the EN cohort will be administered as indicated in Table 4.5.2-2.

Table 4.5.2-2:Dexamethasone Dosing: EN Cohort

Age	Day	1	8	15	22	
Cycles 1 and 2						
All subjects	Dexamethasone (mg)	8 mg IV ^{a,b}				
Cycles 3 and beyond						
All subjects	Dexamethasone (mg)	8 mg IV ^{a,b}				

^a On days of elotuzumab, dexamethasone will be administered as a premedication at dose of 8 mg IV at least 45 minutes before the start of infusion)

^b If elotuzumab dosing is skipped or discontinued, dexamethasone will be not be administered.

4.5.3 Elotuzumab

Elotuzumab will be administered intravenously at a dose of 10 mg/kg weekly (Days 1, 8, 15, and 22 of a 4-week cycle) of the first 2 cycles and starting Cycle 3, elotuzumab will be administered intravenously at a dose of 20 mg/kg of Day 1 of each cycle. A window of -1 to +3 days is permitted in Cycles 1 and 2.

In Cycle 1 and 2, an elotuzumab dose that falls outside of the pre-specified window must be skipped.

In Cycles 3 and beyond, elotuzumab dosing may be delayed for up to 1 week as clinically indicated. If unable to administer within 1 week, then the dose should be skipped and resumption of the elotuzumab continues per the protocol defined schedule.

4.5.3.1 Premedication Before Elotuzumab in Subjects Without a Prior Infusion Reaction

On weeks of elotuzumab infusion, the dexamethasone dose for the EPd cohort will be split into a PO and IV administration (described in Section 4.5.2), which will also serve as premedication for elotuzumab.

Intravenous and PO dexamethasone doses are calculated to provide a total dose that is bioequivalent to an oral dose of 40 mg (subjects who are \leq 75 years old) or 20 mg (in subjects who are > 75 years old). (Dexamethasone 8 mg IV is approximately bioequivalent to 11 mg PO).

For the EN cohort, dexamethasone will still be administered as a premedication for elotuzumab at a dose of 8 mg IV 45-90 minutes prior to initiating the elotuzumab infusion.

In addition, the following must also be administered 45 to 90 minutes before initiating the elotuzumab:

- H1 blocker: diphenhydramine (25 50 mg PO or IV) or equivalent
- H2 blocker: ranitidine (50 mg IV) or equivalent (eg, 150 mg PO)
- Acetaminophen (650 1000 mg PO)

4.5.3.2 Elotuzumab Premedication Regimen in Subjects With a Prior Infusion Reaction

To be re-treated with elotuzumab, subjects with a prior infusion reaction must receive H1, H2 blockers and acetaminophen at maximum doses specified (ie, 50 mg diphenhydramine, 50 mg ranitidine [or equivalent], and 650-1000 mg acetaminophen) 45 to 90 minutes before initiating the elotuzumab.

Recommended dexamethasone dosing is summarized in Table 4.5.3.2-1.

Decisions to use more aggressive premedication schemes in subjects with prior Grade 1 infusion reactions or only one prior Grade 2 infusion reaction must be approved by the Medical Monitor.

	For Subjects ≤ 75 years old	For Subjects > 75 years old			
Prior Infusion Reaction	Corticosteroid Premedication ^a Before Elotuzumab				
None or Only Grade 1 infusion reaction ^b	28 mg po dexamethasone (3 - 24 hrs before elotuzumab) AND 8 mg IV dexamethasone at least 45 min before elotuzumab	8 mg po dexamethasone (3 - 24 hrs before elotuzumab) AND 8 mg IV dexamethasone at least 45 min before elotuzumab			
Prior Grade 2 infusion reaction ^c	28 mg po dexamethasone (3 - 24 hrs before elotuzumab) AND 10 mg IV dexamethasone at least 45 min before elotuzumab	8 mg po dexamethasone (3 - 24 hrs before elotuzumab) AND 10 mg IV dexamethasone at least 45 min before elotuzumab			
Prior Grade 3 or recurrent Grade 2 infusion reaction	8 mg oral dexamethasone (12 - 24 hrs before elotuzumab) AND 8 mg oral dexamethasone (at least 3 hrs before elotuzumab, on the same day as the infusion) AND 18 mg IV dexamethasone at least 45 min before elotuzumab	2 mg oral dexamethasone (12 - 24 hrs before elotuzumab) AND 2 mg oral dexamethasone (at least 3 hrs before elotuzumab, on the same day as the infusion) AND 12 mg IV dexamethasone at least 45 min before elotuzumab			

Table 4.5.3.2-1: Corticosteroid Premedication

For prior infusion reactions, use maximum doses H1, H2 blockers and acetaminophen as described in Section 4.5.3.1.

^a At the discretion of the investigator, the oral dexamethasone component may be given as a split dose 12-24 and 3 hours before elotuzumab.

^b Subjects with prior Grade 1 infusion reaction may be pre-medicated as per Grade 2 infusion reactions.

^c Subjects with prior Grade 2 infusion reaction may be pre-medicated as per Grade 3 infusion reactions.

If a subject with a prior Grade 2 to 3 infusion reaction also requires dose reduction of dexamethasone, the dexamethasone dose on the days of elotuzumab infusion should be no less than 8 mg IV (on the day of elotuzumab infusion at least 45 minutes before elotuzumab).

Subjects with Grade 4 infusion reaction are not eligible to receive additional elotuzumab. These subjects may continue to receive pomalidomide and dexamethasone.

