4.5 Selection and Timing of Dose for Each Subject

Table 4.5-1: Treatment Schedule for EPd Cohort and Cross over Patients from EN Cohort

Cycle	Cycle 1				Cycle 2			Cycle 3 and beyond ^b				
Day	1	8	15	22	1	8	15	22	1	8	15	22
Elotuzumab	10 mg/kg	20 mg/kg										
Dexamethasone ^a	Ļ	Ļ	Ļ	Ļ	Ļ	Ļ	Ļ	Ļ	Ļ	Ļ	Ļ	Ļ
Pomalidomide	Days 1-21				Days 1-21			Days 1-21				
^a See Table 4.5.2-1 for the dose of dexamethasone.												
^b Patients who cross over from the EN cohort will follow the treatment schedule for Cycle 3 and beyond												

Table 4.5-2:Treatment Schedule for the EN Cohort

Cycle	Cycles 1 and 2			Cycles 3 and 4			Cycle 5 and beyond					
Day	1	8	15	22	1	8	15	22	1	8	15	22
Elotuzumab	10 mg/kg	10 mg/kg	10 mg/kg	10 mg/kg	20 mg/kg				20 mg/kg			
Nivolumab	240 mg		240 mg		240 mg		240 mg		480 mg			

See Table 4.5.2-2 for dexamethasone IV dose administered as pre-medication for elotuzumab

4.5.1 *Pomalidomide*

Pomalidomide 4 mg will be administered orally once daily for the first 3 weeks of a 4-week cycle. Pomalidomide should be taken without food (at least 2 hours before or 2 hours after a meal). Subjects should not break, chew or open the capsules.

On the days of elotuzumab administration, the dose of pomalidomide is to be administered at least 2 hours after completion of elotuzumab dosing.

Pomalidomide delay should be performed as clinically indicated at the discretion of the investigator.

Subjects should be instructed that if a dose of pomalidomide has been missed and it has been less than 12 hours since the subject's regular dosing time, to take pomalidomide as soon as the subject remembers. If it has been more than 12 hours, the dose must be skipped. Subjects should not take 2 doses at the same time

Females of reproductive potential must have negative pregnancy testing and use contraception methods before initiating pomalidomide.

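### For EN subjects with a prior elotuzumab infusion reaction, the protocol gives two conflicting dexamethasone premedication doses and does not say which governs; SAP Table 3 carries the conflict forward

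*Protocol*

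**What the plan says.** Three places in the protocol set dexamethasone for the EN cohort, and they agree on the dose.

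- Section 4.5, note to the EN schedule (Table 4.5-2): "See Table 4.5.2-2 for dexamethasone IV dose administered as pre-medication for elotuzumab".
- Section 4.5.2: "Dexamethasone for subjects in the EN cohort will be administered as indicated in Table 4.5.2-2". Table 4.5.2-2 has a single row for all subjects, with no split by age and none by prior reaction. Its footnote a reads: "On days of elotuzumab, dexamethasone will be administered as a premedication at dose of 8 mg IV at least 45 minutes before" the infusion starts.
- Section 4.5.3.1, which covers subjects without a prior reaction: "For the EN cohort, dexamethasone will still be administered as a premedication for elotuzumab at a dose of 8 mg IV".

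Section 4.5.3.2 covers subjects with a prior reaction and states: "Recommended dexamethasone dosing is summarized in Table 4.5.3.2-1". That table has one column for age 75 or under and one for over 75. It has no cohort column, and nothing limits it to EPd. Its first row is labelled "None or Only Grade 1 infusion reaction" and gives the same split oral and IV dose that Table 4.5.2-1 gives EPd subjects on infusion days. The other two rows cover a prior Grade 2 reaction, and a prior Grade 3 or recurrent Grade 2 reaction. Both also combine oral and IV doses.

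SAP Section 7.4.1.10 converts IV to oral dexamethasone at 1.32. Its Table 3 prints the EPd grid under a title that covers every subject receiving elotuzumab. The planned doses it then states are the EPd ones, and none is given for EN.

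**The concern.** After a Grade 2 or 3 reaction, Table 4.5.3.2-1 is the only steroid guidance in the protocol that depends on the reaction, so a site re-treating an EN subject is led to it. Table 4.5.2-2, which has no exception, tells the same site something else. Two sites could treat the same EN subject differently, and each could claim to have followed the protocol.

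The cross-references do not settle it. Section 4.5.5.2 sends re-treatment premedication to Section 4.5.3.1, the section for subjects who have not reacted. Appendix 3 sends premedication to Section 4.5.4, which is about nivolumab.

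Dexamethasone is a treatment component of EPd. In EN it is meant as premedication only, and the EN primary endpoint is ORR. An uncontrolled difference in steroid dose between EN subjects is therefore worth removing, and the SAP's exposure summary should be able to show it if it occurs.

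**Working it through.** **Inputs.** Doses come from Protocol Tables 4.5.2-1, 4.5.2-2 and 4.5.3.2-1. The conversion factor is 1.32 (SAP 7.4.1.10). Oral-equivalent = oral mg + 1.32 × IV mg.

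**The SAP's own figures.** 28 + 8 × 1.32 = 38.56 mg (75 or under) and 8 + 8 × 1.32 = 18.56 mg (over 75). Both match the SAP.

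**EN rule.** 8 × 1.32 = 10.56 mg per infusion, at any age.

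**Table 4.5.3.2-1, per infusion.**

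| Prior reaction | Age | Oral + IV (mg) | Oral-equivalent (mg) | Ratio to 10.56 |
|---|---|---|---|---|
| None or Grade 1 | ≤ 75 | 28 + 8 | 38.56 | 3.65 |
| Grade 2 | ≤ 75 | 28 + 10 | 41.20 | 3.90 |
| Grade 3 or recurrent Grade 2 | ≤ 75 | 16 + 18 | 39.76 | 3.77 |
| None or Grade 1 | > 75 | 8 + 8 | 18.56 | 1.76 |
| Grade 2 | > 75 | 8 + 10 | 21.20 | 2.01 |
| Grade 3 or recurrent Grade 2 | > 75 | 4 + 12 | 19.84 | 1.88 |

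The protocol's own conversion in Section 4.5.3.1 (8 mg IV to 11 mg oral, a factor of 1.375) gives ratios of 3.55 to 3.80 at 75 or under and 1.73 to 1.98 above 75. The choice of factor does not matter.

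**Per cycle, none/Grade 1 row.**

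- Cycles 1 and 2 (four infusions), 75 or under: 4 × 38.56 = 154.24 mg by the table, the same as EPd, against 4 × 10.56 = 42.24 mg by the EN rule. Over 75: 4 × 18.56 = 74.24 mg, again the same as EPd, against 42.24 mg.
- Cycle 3 onward (one infusion), 75 or under: 38.56 mg by the table against 38.56 + 3 × 40 = 158.56 mg for EPd, or 24%. Over 75: 18.56 against 18.56 + 3 × 20 = 78.56 mg, also 24%. The EN rule gives 10.56 mg.

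**Relative dose intensity if SAP Table 3 is applied to EN.** For an EN subject who follows Table 4.5.2-2 in Cycles 1 and 2: 10.56/38.56 = 27% (75 or under) and 10.56/18.56 = 57% (over 75). Both fall in the SAP's lowest category, below 60%. An EN subject given the first-row dose of Table 4.5.3.2-1 would show 100%.

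**ORR.** With 30 subjects, one response is 1/30 = 3.3 percentage points. The documents give no infusion-reaction rate for EN and no response rate to dexamethasone in this population, so the number of affected responses cannot be derived.

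**The case against.** The best defence is that the EN dose is stated three times. For subjects with no reaction, Section 4.5.3.1 names the EN cohort outright. Section 4.5.3.2 is headed for subjects with a prior reaction, so its first row, as far as it covers no reaction, lies outside the section's own scope. The text after the table says that subjects with a Grade 4 reaction may continue pomalidomide and dexamethasone, which reads as if written for EPd. The SAP analyses the cohorts separately (7.1), lists IV and oral dexamethasone by subject (7.4.1.9) and summarises cumulative dose (7.4.1.10), so departures would leave a trace.

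Much of this stands. The first row contradicts the EN text on its face, but the explicit EN sentence makes misapplication less likely in subjects who have not reacted. The Grade 4 sentence hints at EPd drafting without saying so. The listings do exist. None of it tells a site which table applies to an EN subject after a reaction. The relative dose intensity summary would also mislead, because the subject who kept to the EN rule would look under-dosed.

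A reader might infer more than the documents support:

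- *EN subjects receive EPd-level steroid throughout.* Only Cycles 1 and 2 come close. From Cycle 3 the first row is about 24% of the EPd cycle dose, because no steroid is added in weeks without elotuzumab.
- *Exposure could reach 8 × 41.2 = 329.6 mg over Cycles 1 and 2.* It could not. Section 3.3.2 excludes prior elotuzumab from EN, so no EN subject has a prior elotuzumab reaction at the first infusion.
- *The extra steroid breaches the EN steroid exclusion.* That criterion governs the period before study drug starts. It does not regulate premedication on treatment.
- *EN responses cannot be attributed to EN.* EN already includes dexamethasone premedication, and only subjects given the larger dose are in question.

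**Conclusion.** The protocol is inconsistent as written. For an EN subject with a prior elotuzumab infusion reaction, Table 4.5.2-2 and Table 4.5.3.2-1 give different dexamethasone doses, and no text ranks them. Per infusion the gap is 10.56 mg oral-equivalent against 38.56 to 41.2 mg at 75 or under (3.7 to 3.9 times), or 18.56 to 21.2 mg above 75 (1.8 to 2.0 times). These sizes rest on the SAP factor of 1.32 and on a site applying Table 4.5.3.2-1 to an EN subject. How often that happens is unknown.

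The documents do not support a claim that the EN ORR is biased by any particular amount, or that subjects without a reaction are likely to be dosed from the wrong table. The SAP part is separate: Table 3 is mislabelled for EN and no EN planned dose is given. The 27% and 57% figures assume that the dexamethasone intensity summary is run for EN against that table, which its title implies.

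**What to change.** In the protocol, reconcile the note to Table 4.5-2, Table 4.5.2-2, Section 4.5.3.1 and Table 4.5.3.2-1 by cohort. State which table governs EN subjects without a prior reaction and which governs them after one, and label Table 4.5.3.2-1, including its first row, accordingly. The dose is the sponsor's decision. Correct the premedication cross-references in Section 4.5.5.2 and Appendix 3 at the same time.

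In the SAP, relabel Table 3 by cohort and add to Section 7.4.1.10 an EN planned dexamethasone dose that matches the reconciled protocol. From the by-subject dexamethasone listings already planned in Section 7.4.1.9, identify EN subjects who received more than the reconciled EN dose before their best response.

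The cost is a table label, a governing sentence and corrected references in the protocol, and a title, a planned dose and one flag on an existing listing in the SAP. No new data are needed.

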4.5.3.3 Elotuzumab Infusion Rate

During the first cycle, the elotuzumab infusion rate will be increased gradually to a maximum of 5 mL/min as presented in the table below. An infusion rate increase to the next higher level is permitted only if no infusion reactions are encountered.

Infusion Rate	Duration of infusion	Volume delivered	Volume remaining
Cycle 1 Dose 1	Approximate Total D	uration: 2hrs 50min	262 mL*
0.5 mL/min	30 min	15 mL	247 mL
1 mL/min	30 min	30 mL	217 mL
2 mL/min	110 min	217 mL	0 mL
Cycle 1 Dose 2	Approximate Total D	Ouration: 1hr 13min	262 mL
3 mL/min	30 min	90 mL	172 mL
4 mL/min	43 min	172 mL	0 mL
Cycle 1 Dose 3 and 4	Approximate Total	Duration: 53min	262 mL
5 mL/min	53 min	262 mL	0 mL
Cycle 2 +	Approximate Total	Duration: 53min	262 mL
5 mL/min	53 min	262 mL	0 mL

Table 4.5.3.3-1:	Elotuzumab	Infusion	Rate

* Volume for 80 kg subject. Total volume varies according to the subject weight.

Please note that infusion rate increase to the next higher level only if no infusion reactions encountered.

4.5.4 Nivolumab

Nivolumab will be administered at a dose of 240 mg as an intravenous infusion over 30 minutes every 2 weeks (Days 1 and 15 of each 28 day cycle) during Cycles 1 through 4. Starting Cycle 5 and beyond, nivolumab will be administered at a dose of 480 mg as an intravenous infusion over 30 minutes every 4 weeks (Day 1 of each 28 day cycle).

Nivolumab should be administered before elotuzumab.

When administering Q2W, subjects may be dosed no less than 12 days from the previous dose. There are no premedications recommended for nivolumab on the first cycle.

Nivolumab can be delayed within a 3 day window of Day 1 and Day 15, during cycles 1 through 4, as long as the 12 day interval between 2 nivolumab doses is respected.

When administering Q4W, subjects may be dosed no less than 21 days from the previous dose. During cycles 5 and beyond, nivolumab can be delayed within a week.

Doses that fall outside the allowed window, regardless of the schedule, should be skipped.

Subjects should be carefully monitored for infusion reactions during nivolumab administration. If an acute infusion reaction is noted, subjects should be managed according to Section 4.5.6.

There will be no dose escalations or reductions of nivolumab allowed. Doses of nivolumab may be interrupted, delayed, or discontinued in accordance with Section 4.5.8 depending on how well the subject tolerates the treatment.

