3. INVESTIGATIONAL PLAN

3.1 Study Design and Duration

This is a Phase 2, multi-center, open-label, multiple cohort study of elotuzumab in combination with pomalidomide and low-dose dexamethasone (EPd Cohort) and elotuzumab in combination with nivolumab (EN Cohort) to assess the safety and efficacy of these combination therapies for treatment of relapsed or refractory MM patients.

In the EPd Cohort, subjects will receive treatment with elotuzumab in combination with pomalidomide and low-dose dexamethasone in a 28 day cycle. Subjects will receive 10 mg/kg IV elotuzumab on Days 1, 8, 15, and 22 of Cycles 1 and 2. Starting with Cycle 3, subjects will receive 20 mg/kg on Day 1.

As of Amendment 02, subjects will also be enrolled in the EN cohort to receive a combination of elotuzumab and nivolumab in a 28-day cycle. EN subjects will receive nivolumab 240 mg IV on Days 1 and 15 for Cycles 1-4. At Cycle 5 and beyond, subjects will receive 480 mg IV on Day 1. Subjects will also receive elotuzumab 10 mg/kg on Days 1, 8, 15, and 22 of Cycles 1 and 2. At Cycle 3 and beyond, subjects will receive 20 mg/kg of elotuzumab IV on Day 1. If subjects do not achieve clinical benefit represented by at least minimal response (\geq MR) after 2 cycles of treatment or do not achieve an objective response (\geq PR) after 5 cycles of treatment, they may cross over to the EPd cohort at Day 1 of the subsequent cycles if they also meet the eligibility criteria for cross-over specified in Section 3.3.4.

Subjects will continue treatment as long as the subject has clinical benefit from the treatment and do not meet criteria for discontinuation.

All subjects will be assessed for safety and response as presented in the Time and Event Tables in Section 5. Subjects who are discontinued from further study treatment for reasons other than progression will be followed for disease progression. Following disease progression, subjects will be followed at least annually for survival.

Approximately 120 subjects will be screened in this study. A minimum of 60 subjects will be treated in the EPd Cohort. Approximately 30 subjects will be treated in the EN Cohort. The estimated duration of enrollment is 18 to 24 months, and the duration of the study is estimated at 48 months from the date of first patient, first visit. Per Revised Protocol 03, the EPd cohort is closed for enrollment.

The study design schematic is presented in Figure 3.1-1.

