4.5.8 Dose Delay, Interruption, or Discontinuation for All Subjects

Please refer to Sections 4.5.8.1, 4.5.8.2, 4.5.8.3, and 4.5.8.4 for drug-specific delay guidance.

For each cohort, if the dose of one drug in the regimen (ie, pomalidomide, dexamethasone, nivolumab, or elotuzumab) is delayed, interrupted, or discontinued, the treatment with the other drugs may continue as scheduled. However, in the EPd cohort, if dexamethasone is delayed or discontinued discuss ongoing elotuzumab administration with the Medical Monitor. Subjects experiencing a 56 day delay in all study drugs due to an adverse event(s) related to study treatment must be discontinued from study drug. Subjects experiencing delays unrelated to study therapy, for example due to radiation therapy, may delay study treatment after discussion with the medical monitor.

Each cycle is 28 days. While dose delays or interruptions are permitted, the start of each cycle cannot be delayed and is fixed (ie, anchored) relative to Cycle 1 Day 1. Adjustments to the Cycle 1 Day 1 anchored schedule should not be performed. Missed doses should be skipped, not delayed, if not given within the allowed window.

Subjects may continue on study therapy even if components of the study therapy must be discontinued. For example, a subject may continue on study therapy if elotuzumab must be discontinued for an adverse event or other reason. Patients are considered still on study therapy even if they continue solely on pomalidomide, dexamethasone, or nivolumab.

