The relative dose intensity of dexamethasone is the dose intensity per week divided by the planned dose intensity per week times 100%. The planned dose of dexamethasone (indicated in table 3) on elotuzumab dosing days, 8 mg IV dexamethasone plus 28 mg oral dexamethasone, is equivalent to 38.56 mg of oral dexamethasone for subjects \leq 75 years old; similarly for subjects

> 75 years old, the planned dose on elotuzumab dosing days, 8 mg IV dexamethasone plus 8 mg oral dexamethasone, is equivalent to 18.56 mg of oral dexamethasone. The planned dose when dexamethasone is not being administered with elotuzumab is 40 mg per week for subjects \leq 75 years old and 20 mg per week for subjects > 75 years old.

Nivolumab:

The dose intensity (mg/week) of Nivolumab, per subject, will be calculated separately for the period encompassing Cycles 1 to 4 and for the periods from Cycles 5 and beyond.

Cycle 1-4:

7x[cumulative dose of Nivolumab during the first 4 cycles/ (min(date of first dose of Nivolumab in the last cycle among the first 4 cycles+28, discontinuation date, death date) - date of first dose of Nivolumab in cycle 1)]

Cycle 5 and beyond:

7x[cumulative dose of Nivolumab staring from Cycle 5 / (min(date of first dose of Nivolumab in the last cycle+28, discontinuation date, death date) - date of first dose of Nivolumab in cycle 5)]

The relative dose intensity of nivolumab is the dose intensity per week divided by the planned dose intensity per week, 120mg times 100%.

Descriptive statistics (n, mean, STD, median, min, max, q1 and q3) will be presented for the cumulative dose, and dose intensity of each agent. The number and percentage of subjects whose relative dose intensity falls into the following categories will be presented: \geq 90 %, 80% to < 90%, 70% to < 80%, 60% to < 70%, < 60%.

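### The 21-day minimum for four-weekly nivolumab forbids the first 480 mg dose on its scheduled day, 14 days after the last 240 mg dose

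*Protocol*

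**What the plan says.** Protocol section 3.1 sets the EN schedule: "EN subjects will receive nivolumab 240 mg IV on Days 1 and 15 for Cycles 1-4", and then "At Cycle 5 and beyond, subjects will receive 480 mg IV on Day 1". Sections 4.3.2 and 4.5.4 and Table 4.5-2 agree. Section 4.5.8 adds that "the start of each cycle cannot be delayed and is fixed (ie, anchored) relative to Cycle 1 Day 1".

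Section 4.5.4 gives spacing rules for each schedule:

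- **Two-weekly dosing (Cycles 1 to 4).** A dose may be up to 3 days late, "as long as the 12 day interval between 2 nivolumab doses is respected".
- **Four-weekly dosing (Cycle 5 onward).** "subjects may be dosed no less than 21 days from the previous dose". On lateness: "During cycles 5 and beyond, nivolumab can be delayed within a week".
- **Both schedules.** "Doses that fall outside the allowed window, regardless of the schedule, should be skipped".

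No section exempts the first 480 mg dose from the 21-day minimum or sets a separate minimum for the change of schedule.

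**The concern.** At Cycle 5 Day 1 the subject is on the four-weekly schedule, and the previous dose is the 240 mg given on Cycle 4 Day 15. As worded, the 21-day minimum applies to that interval, which the schedule fixes at 14 days. A site cannot follow both instructions. It must dose on schedule and break the spacing rule, delay by a full week, or omit the dose, and different sites may choose differently.

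Each way of obeying the spacing rule has a cost:

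- **Delay to Day 8.** From Cycle 5, Table 5.1-6 marks on-treatment assessments on Day 1 only. Elotuzumab is due on Day 1, and section 4.5.4 wants nivolumab given before it, so elotuzumab must also move or the order is reversed.
- **Omission.** A subject considered for crossover for lack of a partial response after 5 cycles (section 3.3.4) would have had nivolumab in only four of them. The Cycle 5 onward dose-intensity formula in SAP section 7.4.1.10 would also have no start date, because it counts from the "date of first dose of Nivolumab in cycle 5".

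**Working it through.** The plan states no derived figure to reproduce here. The check is calendar arithmetic on the rules above.

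**Study days.** Study day = (cycle − 1) × 28 + day.

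- Cycle 4 Day 1: 3 × 28 + 1 = 85
- Cycle 4 Day 15: 3 × 28 + 15 = 99
- Cycle 5 Day 1: 4 × 28 + 1 = 113
- Cycle 5 Day 8: 4 × 28 + 8 = 120
- Cycle 6 Day 1: 5 × 28 + 1 = 141

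**On-schedule interval at the switch.** 113 − 99 = 14 days, which is 21 − 14 = 7 days short.

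**All permitted combinations.** Let the Cycle 4 Day 15 dose be *a* days late (0 to 3) and the Cycle 5 dose *b* days late (0 to 7). The interval is (113 + *b*) − (99 + *a*) = 14 + *b* − *a*.

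| Cycle 4 Day 15 late by | Interval over Cycle 5 Days 1–8 | Days of 8 with interval ≥ 21 | Days of 8 with interval ≥ 12 |
|---|---|---|---|
| 0 days | 14–21 | 1 (Day 8 only) | 8 |
| 1 day | 13–20 | 0 | 8 |
| 2 days | 12–19 | 0 | 8 |
| 3 days | 11–18 | 0 | 7 |

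The 21-day minimum needs *b* − *a* ≥ 7. Only *a* = 0 with *b* = 7 satisfies this: 1 of 4 × 8 = 32 combinations. A 12-day minimum at the switch would be met in 8 + 8 + 8 + 7 = 31 of 32.

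**Gap if the Cycle 5 dose is skipped.** 141 − (99 + *a*) = 42 − *a*. This gives 41, 40 or 39 days for *a* = 1, 2 or 3, the cases in which no compliant day exists.

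**Where the rules do fit.**

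- Two-weekly doses on schedule are 14 days apart, against a minimum of 12.
- Four-weekly doses on schedule are 28 days apart. After a dose delayed the full week, the next on-time dose follows at 28 − 7 = 21 days. The figure of 21 is therefore exactly what consecutive 480 mg doses with a one-week window require.
- A subject who skipped Cycle 4 Day 15 after an on-time Cycle 4 Day 1 reaches Cycle 5 Day 1 at 113 − 85 = 28 days and complies.

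The conflict is confined to the switch.

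**The case against.** The best reply is that the two minimums are parallel rules, each governing its own dosing interval. On that reading the interval ending at Cycle 5 Day 1 was opened by a 240 mg dose and falls under the 12-day rule. The 480 mg dose on Day 1 from Cycle 5 is stated in several places, and a general spacing sentence should not override it. Section 4.5.4 also rules out raising or lowering the nivolumab dose. Read as literally, that would forbid the move to 480 mg altogether, so these rules are evidently meant to work within the schedule. That is very likely the intent. It is not the wording, however: the rule runs from the previous dose, whatever its size.

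A second reply is that the skip rule covers only doses outside the window, and Cycle 5 Day 1 is inside it. But after a late Cycle 4 Day 15 the 21-day rule bars every day inside the window, and the skip rule removes the days after it. Taken together, and literally, they leave no Cycle 5 dose.

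Several limiting points stand:

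- The gap in the SAP formula arises for anyone who misses the Cycle 5 dose for any reason and later resumes. Correcting section 4.5.4 does not close it.
- A gap of 39 to 41 days is below the 8-week (56-day) limit for stopping nivolumab.
- Only subjects who received Cycle 4 Day 15 and continue nivolumab into Cycle 5 are affected, out of about 30 in the EN cohort.
- The documents give no clinical support for 12 days before a 480 mg dose in particular.

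**Conclusion.** The concern holds. For a subject treated exactly on schedule, a written dosing rule forbids the first 480 mg dose on its scheduled day by a margin of 7 days. One of the 32 permitted timing combinations meets the rule, and none does once the Cycle 4 Day 15 dose is a day or more late. This rests on reading the previous dose as the last nivolumab dose of any size, and on counting the allowed lateness in whole days: 0 to 3 for Cycle 4 Day 15 and 0 to 7 for Cycle 5.

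It is an inconsistency in dosing instructions with a recoverable intent. Sample size, power and the ORR definition are unchanged. So is the timing of the ORR analysis, whose treatment requirement of at least 3 cycles comes before the switch. The text should be corrected because the literal reading costs a delay or a dose and invites inconsistent handling across sites.

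**What to change.** In Protocol section 4.5.4, state that the 21-day minimum applies between consecutive 480 mg doses. Add that the first 480 mg dose, due on Cycle 5 Day 1, must come at least 12 days after the last 240 mg dose, or give another minimum that the sponsor justifies clinically.

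With 12 days, a subject on schedule complies at 14 days. A subject whose Cycle 4 Day 15 dose was 3 days late (11 days to Cycle 5 Day 1) needs a 1-day delay, well inside the window. The rule for later 480 mg doses is unchanged.

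The cost is one or two sentences, with no extra data, visits or procedures. The missing start date in the SAP formula after a skipped Cycle 5 dose needs its own correction.
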